## Research Question and Aims

**Hypothesis:** Healthcare providers (HCP) often deal with patients who are experiencing a variety of ailments, symptoms, and infections at the time of the face-to-face visit. There is an inherent stress that exists when one realizes the life of another being rests in their hands and capabilities. In addition, whereas the risk of contracting diseases in the course of caring for others has always existed, it has never been more evident than during this time of the Covid19 pandemic. The stress of caring for others while worrying about the potential ramifications of their care management decisions and the possibility of contracting Covid19 and inadvertently passing said disease to others (friend and family included) has significant physical and mental health ramifications for HCP. Whereas it has been touted that mindfulness can be a benefit to physicians in the front line, little guidance exists as to how this can be learned and practiced by HCP during such a busy time with little respite. We postulate that using a novel biofeedback-assisted meditation device (Muse-S™) often during the workday can provide mindfulness training to increase calm state brain activity in physicians during a busy practice in the midst of a pandemic. We hypothesize that the greater amount of time the HCP uses this tool, the greater amount of resilience s/he builds, providing needed mental support.

### **Aims, purpose, or objectives:**

1. To study the feasibility of HCP using a wearable brain sensing wellness device (Muse-S™) during a time of increased workload, patient volume and stressors.
2. To assess the association between duration of active state and calm state as measured by the wearable brain sensing wellness device (Muse-S™), and quality of life (QOL), subjective stress, sleep and resilience.

The primary outcome will be the adherence to the Muse-S™ by summarizing the frequency of use and duration of use each time it was accessed.

The secondary outcomes will include:

- change in stress score over time
- measures of QOL, resilience and coping score in HCP at specific time points post baseline.

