Integrative Medicine has introduced many mind-body therapies for addressing mental stress. The top stress relievers recommended by Mayo Clinic include: getting active, eating a healthy diet, avoiding unhealthy habits, meditation, laughing more, connecting with others, asserting yourself, practicing yoga, getting enough sleep, keeping a journal, exploring music and being creative, seeking counseling. Among all of these potential options, meditation is the easiest to incorporate in a current lifestyle yet most difficult to undertake without proper training and guidance at the beginning. Muse-S™ is a clinical grade, headband-style wireless EEG system designed to interact with a mobile device (a smartphone or tablet) (<https://choosemuse.com>). In combination with the Muse-S™ APP running on iOS or Android smartphones, Muse-S™ converts EEG signals measured over the frontal and temporal cerebral cortices into measures of brain state. At the same time Muse-S™ can also guide the user through the meditation steps. Calibrated to an individual user, Muse-S™ distinguishes between active and calm brain states to provide real-time performance feedback, and helps users realize the benefits of mindfulness practice in an engaging and accessible manner. Muse-S™ also has a PPG sensor that tracks heartrate during meditation sessions as well. This has been tested in a prior study by some of the current study team ([name]), with patients undergoing breast cancer surgery.

[figure not shown]

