**Study Design and Methods**

**Methods:**

All study participants will receive the Muse S™ Headband system at study entry and will be asked to utilize it at least 4 times per week for a minimum of 10 minutes each time over a period of 3 months (12 weeks). They will be followed for a period of 6 months (3 months of treatment and 3 months post treatment) according to the schedule below.

We will assess the following:

- Type of meditation the patient has selected from the 3 available options: Mind Meditation, Guided Meditation and Go-to-sleep meditation.
- Frequency and duration of use from baseline to month 3 (end of treatment). The participants will be informed at baseline that for best results, it will be recommended that they use it a minimum of 10 minutes, at least 4 times per week for over 3 months. If they are short on time, they can break up the 10 minutes and do shorter meditations.

- Changes in QOL, stress, resilience, and sleep score from baseline through week 2, month 1, month 3 and month 6.

Visit No.	Consent /screen /baseline	Treatment Phase			Follow up Phase
	1	2	3	4	5
Visit Type	face to face	Phone/ email	Phone/ email	face to face/phone/ email	face to face/phone/ email
Visit Days	0	14	30	90	180
Informed Consent	X				
Inclusion/Exclusion	X				
Demographic and History Form	X				
Depression	X	X	X	X	X
Burnout	X			X	X
Resilience	X	X	X	X	X
Sleep	X	X	X	X	X
Quality of Life	X	X	X	X	X
Stress Scale	X	X	X	X	X
Satisfaction Survey					X
Adverse Events 		X	X	X	X
CBS Cognitive Tests	X			X	X
Concomitant Medication 	X	X	X	X	X
Instructions for Muse-S™	X				
End of Treatment/End of Study Forms				X	X

1 = For visit 5, only serious adverse events will be newly collected; 2 = For visit 5, only newly added concomitant medications will be collected

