General Study Information

Principal Investigator: [name]

A Study Title: A Feasibility study evaluating Mindfulness-Based Intervention Assessing A Wearable Wellness Brain Sensing Device (Muse-S™) in Practicing Health Care Providers.

Protocol date: 23 Sept 2024

Data Analysis

Data Analysis Plan:

Demographic characteristics are described using mean and standard deviations or frequencies and percentages based on the type of variable. For the primary aim of assessing feasibility, descriptive statistics and graphical displays will be presented for data obtained on frequency and duration of use over the 12 weeks of treatment. A linear mixed model with repeated measures for each time point that stress and sleep were taken will be utilized to estimate the association between the average of time spent using the Muse-S™ with the stress and sleep level outcome. Age, sex, and the total amount of meditation time at each interval will also be adjusted for in the model. As secondary outcomes, the results of the LASA, resilience, coping, and cognitive testing will be analyzed using linear mixed models with repeated measures to determine changes over time. In all cases, results will be summarized using point-estimates and corresponding 95% confidence intervals. Given the number of outcomes assessed, all analyses will be considered exploratory.

Endpoints:

Primary Hypothesis:

- a) HCP enrolled in this study will find the Muse-S™ Headband system easy to use and will use it often during the work week.

Secondary Hypotheses:

- a) Stress score will be lower and sleep score will be improved when compared to the baseline measures for those who use the Muse-S™ system as directed.
- b) As the use of the Muse-S™ system increases, QOL, resilience and coping will improve.

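### Aim 2's exposure, minutes in calm and active state, mixes amount of use with brain state, and no SAP model contains either state

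*Protocol*

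**What the plan says.** Aim 2 (Protocol, Aims, purpose, or objectives) is "To assess the association between duration of active state and calm state as measured by the wearable brain sensing wellness device", related to quality of life, stress, sleep and resilience. It gives no share, ratio or per-session scale. The hypothesis in Research Question and Aims is that the device "can provide mindfulness training to increase calm state brain activity"; its last sentence adds that more time on the device builds more resilience. The Background section names two states and says they are set per person: "Calibrated to an individual user, Muse-S™ distinguishes between active and calm brain states to provide real-time performance feedback".

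The SAP (Data Analysis Plan) describes two kinds of model:

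- **Stress and sleep:** a linear mixed model to "estimate the association between the average of time spent using the Muse-S™ with the stress and sleep level outcome". It continues: "Age, sex, and the total amount of meditation time at each interval will also be adjusted for in the model".
- **LASA, resilience, coping and cognition:** these "will be analyzed using linear mixed models with repeated measures to determine changes over time". No exposure term is stated.

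Calm and active state do not appear anywhere in the SAP. Its secondary hypothesis (b) is about increasing use of the system.

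**The concern.** The protocol holds two ideas: that a calmer brain state goes with better wellbeing, and that more practice does. Minutes in calm state equal recorded minutes multiplied by the calm share, so the Aim 2 exposure carries both. If calm minutes are related to stress without account of recorded time, a reader cannot say how much of the association belongs to each.

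One would look to the SAP to separate them, but it has no analysis of the Aim 2 exposure. As written, the stress and sleep model answers a question about amount of use. Its exposure (average time of use) and its covariate (total meditation time) measure much the same thing, so that coefficient is itself hard to interpret. For quality of life and resilience no association with the device data is specified. An analyst would have to choose the Aim 2 model after seeing the data, and the obvious choice, raw minutes, is the ambiguous one.

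**Working it through.** The documents give no correlation, effect size or power for Aim 2, so there is no planned figure to reproduce.

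**Inputs from the documents**
- Requested use: 4 sessions × 10 minutes × 12 weeks = 480 minutes at minimum (Methods).
- Sample size: 40 (Target accrual).
- States: two, calm and active (Background).

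**Assumptions, not in the documents**
- Recorded time T has coefficient of variation *a*.
- Calm share p has mean 0.5 and SD 0.10 or 0.20, so its coefficient of variation *b* is 0.2 or 0.4.
- p is independent of T, and every recorded minute is calm or active.

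**Correlations.** Let calm minutes be C = pT, active minutes A = (1 − p)T, and D = a² + b² + a²b². Then
- corr(C, T) = a / √D
- corr(C, p) = b / √D
- corr(C, A) = (a² − b² − a²b²) / D, for mean share 0.5

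For example, with a = 0.5 and b = 0.2, D = 0.25 + 0.04 + 0.01 = 0.30 and √D = 0.548. This gives 0.5/0.548 = 0.91, 0.2/0.548 = 0.37 and (0.25 − 0.04 − 0.01)/0.30 = +0.67.

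| CV of use (a) | SD of share | D | calm vs total | calm vs share | calm vs active |
|---|---|---|---|---|---|
| 0.2 | 0.10 | 0.0816 | 0.70 | 0.70 | −0.02 |
| 0.2 | 0.20 | 0.2064 | 0.44 | 0.88 | −0.61 |
| 0.5 | 0.10 | 0.30 | 0.91 | 0.37 | +0.67 |
| 0.5 | 0.20 | 0.45 | 0.75 | 0.60 | +0.11 |
| 1.0 | 0.10 | 1.08 | 0.96 | 0.19 | +0.85 |
| 1.0 | 0.20 | 1.32 | 0.87 | 0.35 | +0.52 |

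Simulation with lognormal T and beta-distributed p agrees with these formulas to about 0.01 in the settings they share. With a mean share of 30%, the simulated calm–total correlation runs from 0.28 (CV 0.2, SD 0.20) to 0.88 (CV 0.8, SD 0.10).

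**What this does to an association.** Suppose the outcome depends only on total time, with an assumed correlation of −0.4, and brain state has no effect. Calm minutes then correlate with the outcome at −0.4 × corr(C, T): −0.30 at 0.75 and −0.38 at 0.96. The calm share correlates at 0. The table gives the percentage of 2,000 simulated studies of 40 people with two-sided p < 0.05, from a simplified cross-sectional regression (not the planned mixed model) with mean share 0.5:

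| CV of use | SD of share | calm minutes alone | calm minutes, adjusted for total | calm share |
|---|---|---|---|---|
| 0.2 | 0.10 | 43 | 5.1 | 4.8 |
| 0.2 | 0.20 | 20 | 6.4 | 5.4 |
| 0.5 | 0.10 | 63 | 5.4 | 5.0 |
| 0.5 | 0.20 | 46 | 4.9 | 5.1 |
| 0.8 | 0.10 | 64 | 5.1 | 4.8 |
| 0.8 | 0.20 | 53 | 5.3 | 5.6 |

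**Which terms can enter together.** If C + A = T, a design matrix with an intercept, C, A and T has rank 3 of 4, so the three times cannot all be fitted. Any two can.

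**The case against.** The strongest reply is that the SAP already adjusts for total meditation time in the stress and sleep model. If calm minutes were entered there, their coefficient would be conditional on total time, and the simulation shows that this brings a spurious finding back to about 5% to 6%. Likewise, calm and active minutes in one model carry the state effect in the difference of their coefficients, because b₁C + b₂A = b₂T + (b₁ − b₂)C. This stands as a route to a sound analysis, but the SAP does not take it. The covariate is stated only for stress and sleep, and the exposure beside it is average use. Total meditation time may also include guided sessions done without the headband, which the protocol allows and which have no EEG.

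A second reply is that amount of use is a stated interest, in the last sentence of the hypothesis and in SAP secondary hypothesis (b). That is correct, and it is a reason to keep use as a term of its own, not to leave it mixed into the state measure.

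A reader might infer more: that Aim 2 would show amount of use and not brain state, or that calm and active minutes must both appear to help or both to harm. The documents do not support this. They give no variation in use, and everyone is asked for the same minimum schedule. At a CV of 0.2, calm minutes follow the calm share at least as closely as total time, and calm and active minutes correlate between −0.02 and −0.61. The same-sign pattern is expected only in separate, unadjusted models with no state effect and widely varying use.

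**Conclusion.** The point holds in a limited form. The Aim 2 exposure is a mixture of amount of use and brain state, and no SAP model analyses it or separates the two. The mixture leans towards use when people differ widely in practice time, and towards state when practice is uniform and calm share varies. The documents do not show which case applies. In the assumed null example with 40 people, unadjusted calm minutes look associated with the outcome in 20% to 64% of studies, against about 5% to 6% with total time adjusted for or with calm share used. Those rates rest on the assumed −0.4 correlation, independence of share and use, and a cross-sectional model.

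This is a feasibility study with adherence as its primary outcome, and the SAP declares all analyses exploratory. What is at stake is the meaning of the Aim 2 estimate, not error control. It should be settled before the analysis.

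**What to change.** In Aim 2 and the SAP, define the exposure as the share of recorded headband (EEG) time spent in calm state in each interval. Enter recorded headband minutes as a separate term, replacing the overlapping average-use and total-time terms. Use the same specification for stress, sleep, quality of life and resilience. Do not enter calm, active and total minutes together. Leave sessions without the headband out of the denominator. State how intervals with no recorded headband time are handled, because the share is then undefined, and which exposure goes with the month 6 assessment, because Methods assesses use only to month 3.

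Individual calibration affects the share as well as the minutes, so a split of calm share into each person's mean and the deviation from it is a sensible sensitivity analysis. With 40 people and at most three treatment-phase assessments each (days 14, 30 and 90), it is a debatable choice for the main result.

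The cost is a change of wording in two places and a little extra analysis. Server Data already lists session type, session duration, EEG data and performance per session, so no new data source appears necessary.

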### **Background:**

Prior to the COVID 19 pandemic, physicians were experiencing high degree of burnout, which has consequence to physician health. A multitude of causes result in physician burnout, such as adopting/learning new electronic medical records, administrative responsibilities taking time away from clinical practice, lack of autonomy, changes in reimbursement model and other factors.

COVID 19 has added another dimension to the stress experienced by physicians. A recent study in JAMA, showed that front line healthcare workers in China were experiencing a high degree of stress. It was reported that “A considerable proportion of participants reported symptoms of depression (634 [50.4%]), anxiety (560 [44.6%]), insomnia (427 [34.0%]), and distress (899 [71.5%])”. Additional stressors include the rapidly changing way medicine is being practiced. The use of barrier-protection, adoption of telemedicine, and decrease of income has affected the way physicians practice medicine. This along with fear of infection and passing along to family members add additional pressure on physicians.

Integrative Medicine has introduced many mind-body therapies for addressing mental stress. The top stress relievers recommended by Mayo Clinic include: getting active, eating a healthy diet, avoiding unhealthy habits, meditation, laughing more, connecting with others, asserting yourself, practicing yoga, getting enough sleep, keeping a journal, exploring music and being creative, seeking counseling. Among all of these potential options, meditation is the easiest to incorporate in a current lifestyle yet most difficult to undertake without proper training and guidance at the beginning. Muse-S™ is a clinical grade, headband-style wireless EEG system designed to interact with a mobile device (a smartphone or tablet) (<https://choosemuse.com>). In combination with the Muse-S™ APP running on iOS or Android smartphones, Muse-S™ converts EEG signals measured over the frontal and temporal cerebral cortices into measures of brain state. At the same time Muse-S™ can also guide the user through the meditation steps. Calibrated to an individual user, Muse-S™ distinguishes between active and calm brain states to provide real-time performance feedback, and helps users realize the benefits of mindfulness practice in an engaging and accessible manner. Muse-S™ also has a PPG sensor that tracks heartrate during meditation sessions as well. This has been tested in a prior study by some of the current study team ([name]), with patients undergoing breast cancer surgery.

[figure not shown]
**Study Design and Methods**

**Methods:**

All study participants will receive the Muse S™ Headband system at study entry and will be asked to utilize it at least 4 times per week for a minimum of 10 minutes each time over a period of 3 months (12 weeks). They will be followed for a period of 6 months (3 months of treatment and 3 months post treatment) according to the schedule below.

We will assess the following:

- Type of meditation the patient has selected from the 3 available options: Mind Meditation, Guided Meditation and Go-to-sleep meditation.
- Frequency and duration of use from baseline to month 3 (end of treatment). The participants will be informed at baseline that for best results, it will be recommended that they use it a minimum of 10 minutes, at least 4 times per week for over 3 months. If they are short on time, they can break up the 10 minutes and do shorter meditations.

- Changes in QOL, stress, resilience, and sleep score from baseline through week 2, month 1, month 3 and month 6.

Visit No.	Consent /screen /baseline	Treatment Phase			Follow up Phase
	1	2	3	4	5
Visit Type	face to face	Phone/ email	Phone/ email	face to face/phone/ email	face to face/phone/ email
Visit Days	0	14	30	90	180
Informed Consent	X				
Inclusion/Exclusion	X				
Demographic and History Form	X				
Depression	X	X	X	X	X
Burnout	X			X	X
Resilience	X	X	X	X	X
Sleep	X	X	X	X	X
Quality of Life	X	X	X	X	X
Stress Scale	X	X	X	X	X
Satisfaction Survey					X
Adverse Events 		X	X	X	X
CBS Cognitive Tests	X			X	X
Concomitant Medication 	X	X	X	X	X
Instructions for Muse-S™	X				
End of Treatment/End of Study Forms				X	X

1 = For visit 5, only serious adverse events will be newly collected; 2 = For visit 5, only newly added concomitant medications will be collected

**Study Visit Windows:**

Each visit will have a window from midpoint of prior visit to midpoint of latter visit.

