### Outcomes:

- **Demographics Form:** This form collected demographic and other lifestyle history of the research subject.
- **Burnout:** We will measure burnout using 2 single-item measures adapted from the full Maslach Burnout Inventory (MBI). These 2 items have been demonstrated to correlate strongly with the emotional exhaustion and depersonalization domains of burnout measured by the full MBI in a sample of over 10,000 individuals with an area under the ROC curve of 0.94 and 0.93 for emotional exhaustion and depersonalization, respectively, for these single items relative to the full MBI.
- **Quality of Life:** Will be measured using the *Linear Analogue Self-Assessment (LASA)*. This measure is a six-item measure of quality of life (QOL), in which QOL is conceptualized as a multidimensional construct with five domains (physical, functional, emotional, spiritual, and social). This data will be collected at screen (prior to any treatment), day 14, day 30, day 60, end of treatment day 90, and at end of study day 180 (3months post last treatment).
- **Stress:** Will be evaluated through the *Perceived Stress Scale (PSS)*. The PSS is a 10-item Likert scale that measures global life stress by assessing the degree to which experiences are appraised as uncontrollable or unpredictable. Scores can range from 0 to 40, with higher scores indicating greater perceived stress. Reliability is reported as 0.85, with Cronbach alphas ranging from 0.75-0.86.
- **Resilience:** Will be evaluated through the *Connor-Davison Resilience Scale 10 (CD-RS10)*. This is a 10-item, likert scale, validated, scoring system. The CD-RS10 is a reliable means of assessing resilience and most often used in medical and/or disaster studies.
- **Sleep Quality:** *The Pittsburgh Sleep Quality Index (PSQI)* is an effective instrument used to measure the quality and patterns of sleep in adults. This is a 9-item, likert scale, validated, scoring system. It differentiates “poor” from “good” sleep quality by measuring seven areas (components): subjective sleep quality, sleep latency, sleep duration, habitual sleep efficiency, sleep disturbances, use of sleeping medications, and daytime dysfunction over the last month.

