- **Satisfaction with the program:** This questionnaire is adapted from *Was it Worth it Questionnaire (WIWI)* to measure study and Muse-S™ satisfaction. It will be administered to the participants after completing the intervention at the end of the study, probing their satisfaction with the research study. These data could be used to assess the feasibility of the intervention by asking the patient if the entire research experience was worth it for them.

*Adherence to Intervention:*

- **Adherence to the Muse-S™** will be assessed by de-identified data available within the cloud, provided by InteraXon. InteraXon only has information per subject through subject ID only (as was provided by Mayo Clinic site), so when the cloud data is provided to Mayo, it will be linked to each subject through their study ID.

*Intervention:*

- **The Muse-S™ Headband system:** The Muse-S™ Headband system is a brain sensing headband that measures brain activity by detecting electrical impulses created by the brain. The Muse-S™ Headband system uses a series of focus attention training methods to train the brain. Each focus attention session can vary in length, with the ideal being a minimum of 10 minutes, and has been shown to reduce stress, anxiety, and improve focus and productivity. The Muse-S™ Headband system has seven sensors with four channels of EEG data for an accurate, high-quality experience. The battery life is approximately five hours and uses an industry-standard micro-USB charger. Twenty Muse-S™ Headband systems will be provided by the manufacturer at no cost in support of this study.

[figure not shown]
Use of Muse-S™ Headband systems will be demonstrated to each participant prior to their first mindfulness practice session, which will be completed during the baseline visit with the study coordinator. The study coordinator will present the participant with detailed instructions on how to begin each session. The frequency of the sessions thereafter will be at the participant’s discretion according to the study’s requirements (daily practice). Mindfulness training will follow the protocol in the Muse-S™ APP, which follows a standard breathing exercise with EEG brain state feedback through the mobile device, as designed by a panel of experienced mindfulness practitioners. In short, the Muse-S™ is a *FitBit* like device for the brain.

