- **Server Data:** As the subject completes any Muse-S™ sessions, the information from these sessions will be uploaded to the Muse-S™ iCloud servers hosted by Google. Each subject will be able to see their own data at the end of each session, and data from the previous session stored in the “me” tab in the app. Subject to the study organizers ensuring that the subjects have signed the appropriate consents, study organizers will have access to each subject’s data to monitor compliance, performance and outcomes, but will not get access to Journal entry information (if subject chooses to write a Journal entry). These data that the study organizers will have access to can include the study-specific identification number, gender, and age of the subject, the session type, the time and duration of each session, EEG data, heart rate (PPG) data, and the performance per session. Interaxon’s privacy policy, which can be found at [www.choosemuse.com/privacy](http://www.choosemuse.com/privacy) will apply to Interaxon’s use of the subjects’ data. In order to maximize protection of the individual’s privacy, the study organizers will ensure that the subjects

are assigned anonymized email address and names for use in the Muse -S™ application and when contacting the Muse-S™ customer support. To ensure that no health data is shared with Interaxon, the study organizers have agreed to ensure that no health data will be shared with Interaxon. At the end of the study, the data collected in Google ICloud Server associated with study email addresses will be deleted.

- The Muse-S™ steps include: 1) Open the Muse-S™ App on your phone. 2) select meditation type 3) if meditating with the headband, turn on the Muse-S™ headband. It will pair via bluetooth to the app 4) put on headband (if doing a meditation with headband) 5) meditate 6) add any journal or mood entry if desired 7) review results
- Cleaning the Muse-S™: Each patient will be given a brand new, out-of-the-box Muse-S™ Headband system. If cleaning must occur, the entire Muse-S™ including the head set can be wiped down with a standard disinfectant wipe. The band can also be hand-washed gently with soap and water. The module on the band is not waterproof but can be wiped with disinfectant.

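### On schedule, about half of the Day-14 sleep recall precedes treatment, and the SAP does not say how assessment timing within wide visit windows enters the models (minor; secondary outcomes only)

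*Protocol*

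**What the plan says.** **Schedule and windows.** The visit table in the Protocol's Methods sets visits at Days 0, 14, 30, 90 and 180. Sleep, stress, resilience and quality of life are assessed at all five. Study Visit Windows gives one rule: "Each visit will have a window from midpoint of prior visit to midpoint of latter visit".

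**Sleep index.** The Sleep Quality entry under Outcomes ends its list of components with "daytime dysfunction over the last month"; I read the recall period as applying to the whole index. The Intervention section has the device demonstrated "prior to their first mindfulness practice session, which will be completed during the baseline visit". Methods plans to assess "Changes in QOL, stress, resilience, and sleep score from baseline through week 2, month 1, month 3 and month 6".

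**Treatment period.** Methods describes use "over a period of 3 months (12 weeks"), follow-up as "3 months of treatment and 3 months post treatment", and advice to participants of use "at least 4 times per week for over 3 months". The quality-of-life entry under Outcomes labels Day 90 as the end of treatment.

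**Analysis.** The SAP's Data Analysis Plan fits a repeated-measures linear mixed model to stress and sleep at every time they are taken. It relates them to average time on the device and adjusts for age, sex and total meditation time per interval. It does not say whether time is the nominal visit or the actual day, and it does not define the interval.

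**Use data.** Server Data makes available "the session type, the time and duration of each session", and says that the cloud data tied to study email addresses will be deleted at the end of the study. Subject Retention lets participants keep the headband.

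**The concern.** There are two separate timing problems, both affecting what a labelled time point means.

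The first is built into the schedule. A one-month recall taken two weeks after the first session must reach back before that session. If baseline is answered on Day 0, those days are already in the baseline score. A week-2 change then compares two partly shared periods, and a real early change in sleep would tend to look smaller than it is. The same score enters the model relating device use to sleep.

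The second depends on how visits actually fall. Under the window rule, one month-3 label can cover scores taken well before or well after Day 90. Unless the SAP says that actual day is used, the reader cannot tell what has been pooled. The use covariate has a related problem: if the interval runs from visit to visit, total meditation time depends on scheduling as well as on behaviour.

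**Working it through.** The documents give a rule and visit days but no numeric window limits, so there is no stated figure to reproduce.

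**Step 1: windows.** Inputs are the visit days 0, 14, 30, 90, 180 and the midpoint rule, taken between scheduled days (the natural reading; the rule does not say scheduled or actual).

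| Visit | Nominal day | Earliest | Latest |
|---|---|---|---|
| 2 | 14 | (0+14)/2 = 7 | (14+30)/2 = 22 |
| 3 | 30 | 22 | (30+90)/2 = 60 |
| 4 | 90 | 60 | (90+180)/2 = 135 |
| 5 | 180 | 135 | none (no later visit) |

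Visit 4 may therefore fall 90 - 60 = 30 days early or 135 - 90 = 45 days late. The quality-of-life entry also lists a Day-60 assessment that is not in the visit table. If it counts as a visit for that measure, the earliest limit becomes (60+90)/2 = 75 and the latest stays at 135.

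**Step 2: pre-treatment share of the sleep recall.** For a score on day d, with a recall of m days and the first session on Day 0, the share is max(0, m - d)/m. The documents do not give the length of a month in days, so I show 28, 30 and 31.

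| Day of score | m = 28 | m = 30 | m = 31 |
|---|---|---|---|
| 7 (earliest Visit 2) | 21/28 = 75.0% | 23/30 = 76.7% | 24/31 = 77.4% |
| 14 (nominal Visit 2) | 14/28 = 50.0% | 16/30 = 53.3% | 17/31 = 54.8% |
| 22 (latest Visit 2, earliest Visit 3) | 6/28 = 21.4% | 8/30 = 26.7% | 9/31 = 29.0% |
| 30 (nominal Visit 3) | 0 | 0 | 1/31 = 3.2% |
| 60 (earliest Visit 4) | 0 | 0 | 0 |

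Every permitted Visit 2 score has some overlap, and so does an early Visit 3 score. Visits 4 and 5 have none. If the Intervention sentence means that only the demonstration happens at baseline and the first session comes later, the shares rise.

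**Step 3: what the overlap could do (illustration, not an estimate of bias).** Assume that the index weights all recalled nights equally. A sleep change that starts at once would then show at Day 14 as 14/m of its size: 14/28 = 50%, 14/30 = 47%, 14/31 = 45%. A change that builds evenly from Day 0 would show as half of that, 23-25% of its Day-14 level. The documents specify neither the weighting nor the course of the effect.

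**Step 4: the undefined interval.** If it means visit to visit, the interval before Visit 4 is nominally 90 - 30 = 60 days. At the outer limits it runs from almost nothing (Visits 3 and 4 both near Day 60) to 135 - 22 = 113 days.

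**The case against.** Contiguous midpoint windows are a conventional way to keep every assessment. The Treatment phase text plans contact at set days, and Data Collection allows questionnaires online before the visit, which favours early rather than late completion. The SAP's wording is ambiguous and does not exclude actual time, and its adjustment for meditation time covers part of the exposure question. The SAP also labels all analyses exploratory, and the study plans only 40 participants. Stating the recall overlap as a caveat might be enough. Most of this stands, and it is why the point is minor. It does not remove the Day-14 overlap, which occurs even when every visit is on time.

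Some stronger readings are tempting but not supported:

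- *That end-of-treatment scores will in practice be taken off treatment.* Day 135 is only a limit. Headbands are kept, so a late score is not necessarily unexposed, and the window also runs early, to Day 60.
- *That the plan has no defined end of treatment.* Day 90 is labelled as such, and the visit table places that visit in the treatment phase. Twelve weeks is 12 x 7 = 84 days, six days short of 90, and the advice to use the device for longer than three months may be loose wording. This is a matter of reconciling text.
- *That the overlap is 50-55% for everyone.* That holds only on the nominal day.
- *That the month-3 and month-6 sleep changes are biased by the recall overlap.* They need not be, if time points are modelled separately.

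**Conclusion.** The point holds as a minor one. It concerns secondary, exploratory outcomes only; the primary adherence outcome, taken from device records, is untouched.

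The sleep part is the firmer of the two. Following the plan as written likely dilutes the week-2 sleep change and that visit's contribution to the use-sleep association. The pre-treatment share is 50-55% on the nominal day, about 21-77% across the permitted Visit 2 window, and still 21-29% for a Visit 3 score on Day 22. These figures assume a 28- to 31-day recall and a first session on Day 0. How far any estimate would move cannot be derived from the documents.

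The window part is mainly silence in the SAP about a wide outer limit, Days 60 to 135 for the month-3 visit. The number of visits that would fall far from Day 90, and the effect on the results, are unknown.

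**What to change.** **Sleep recall.** Report the Day-14 sleep score descriptively, with the overlap stated. Leave out of the sleep-change and use-sleep estimates any post-baseline sleep score taken less than one recall period after the first session, or show this at least as a sensitivity analysis. State one figure for the recall period, in the range of 28 to 31 days. A figure of 31 would also remove Visit 3 scores taken exactly on Day 30; 28 or 30 would not.

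**Visit timing.** Keep all assessments. State in the SAP that the mixed models use actual study day, and define the interval by counting Muse-S use from session time stamps up to each assessment day. Add a sensitivity analysis that leaves out month-3 scores further from Day 90, on either side, than a distance fixed in advance. If time is fitted as a continuous curve, an early sleep score can pull the curve at later days too, which is a further reason for the sleep exclusion.

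**Wording.** Reconcile the three descriptions of the treatment period: three months given as 12 weeks, use for longer than three months, and Day 90 as the end of treatment.

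**Cost.** A few sentences in the SAP and a wording correction in the Protocol. No data collection is dropped. One early sleep time point, and perhaps a few early Visit 3 sleep scores, leave the model. Counting use after month 3 goes beyond the use period that Methods plans to summarise, so it should be confined to the secondary models. Session times and durations are already recorded, but they must be exported through the last assessment before the planned server deletion.
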